7.1.2 Temporary discontinuation

Temporary intervention discontinuation may be considered by the Investigator because of suspected AEs. For all temporary intervention discontinuations, duration should be recorded by the Investigator in the appropriate pages of the eCRF.

Temporary intervention discontinuation decided by the Investigator corresponds to at least 1 dose not administered to the participant. Following a temporary interruption or missed dose, the treatment should be reinitiated at the next scheduled administration, maintaining the planned dose.

If 2 consecutive IMP doses have been missed, the study treatment will be definitively discontinued (see [Section 7.1.1](#)). Investigator must contact the participant to instruct not to take any subsequent injection.

7.1.2.1 Rechallenge

Reinitiation of intervention with the IMP will be done under close and appropriate clinical/and or laboratory monitoring once the Investigator will have considered according to his/her best medical judgment that the responsibility of the IMP(s) in the occurrence of the concerned event was unlikely and if the selection criteria for the study are still met (refer to [Section 5](#)).

7.2 PARTICIPANT DISCONTINUATION/WITHDRAWAL FROM THE STUDY

- A participant may withdraw from the study at any time at his/her own request or if his/her parent(s)/caregiver(s)/legally authorized representative(s) decide to do so, or may be withdrawn at any time at the discretion of the Investigator for safety, behavioral, compliance, or administrative reasons. This is expected to be uncommon.
- At the time of discontinuing from the study, if possible, an early follow-up/EOS visit should be conducted, as shown in the SoA ([Section 1.3](#)). See SoA for data to be collected at the time of study discontinuation and follow-up and for any further evaluations that need to be completed.
- The participant will be permanently discontinued both from the study intervention and from the study at that time.
- If the participant withdraws consent for disclosure of future information, the Sponsor may retain and continue to use any data collected before such a withdrawal of consent.
- If a participant withdraws from the study, he/she may request destruction of any samples taken and not tested, and the Investigator must document this in the site study records.

All study withdrawals should be recorded by the Investigator in the appropriate screens of the eCRF and in the participant's medical records. In the medical record, at least the date of the withdrawal and the reason should be documented.

In addition, a participant may withdraw his/her consent to stop participating in the study. A participant's decision to discontinue intervention should be distinguished from withdrawal of consent for follow-up visits and from withdrawal of consent for non-participant contact follow-up, eg, medical record checks. The site should document any case of withdrawal of consent.

Participants who have withdrawn from the study cannot be rerandomized (treated) in the study. Their inclusion and intervention numbers must not be reused.

7.3 LOST TO FOLLOW-UP

A participant will be considered lost to follow-up if he or she repeatedly fails to return for scheduled visits and is unable to be contacted by the study site.

The following actions must be taken if a participant fails to return to the clinic for a required study visit:

- The site must attempt to contact the participant and reschedule the missed visit as soon as possible and counsel the participant on the importance of maintaining the assigned visit schedule and ascertain whether or not the participant wishes to and/or should continue in the study.
- Before a participant is deemed lost to follow-up, the Investigator or designee must make every effort to regain contact with the participant (where possible, 3 telephone calls and, if necessary, a certified letter to the participant's last known mailing address or local equivalent methods). These contact attempts should be documented in the participant's medical record.
- Should the participant continue to be unreachable, he/she will be considered to have withdrawn from the study.

Discontinuation of specific sites or of the study as a whole are handled as part of Appendix 1 (Section 10.1).

8 STUDY ASSESSMENTS AND PROCEDURES

- Study procedures and their timing are summarized in the SoA ([Section 1.3](#)). Protocol waivers or exemptions are not allowed.
- Adherence to the study design requirements, including those specified in the SoA, is essential and required for study conduct.
- All screening evaluations must be completed and reviewed to confirm that potential participants meet all eligibility criteria. The Investigator will maintain a screening log to record details of all participants screened and to confirm eligibility or record reasons for screening failure, as applicable.
- Procedures conducted as part of the participant's routine clinical management (eg, blood count) and obtained before signing of the ICF/assent form may be utilized for screening or baseline purposes provided the procedures met the protocol-specified criteria and were performed within the time frame defined in the SoA.
- Assessments/procedures should be conducted in the following order: daily symptoms of nasal congestion; loss of smell and rhinorrhea; SNOT-22; VAS rhinosinusitis; [REDACTED] and administration of IMP. Note:
[REDACTED]
- PRO questionnaires should be completed by the participants (not applicable for children aged ≥ 6 and <12 years) before the consultation and/or clinical tests, in a quiet place (at home in e-diary and at clinic). The questionnaires should be completed by the participants themselves, independently from their physician, the study nurse, or any other medical personnel and without any help from friends or relatives.
- Participants under 18 years of age will have a caregiver or a tutor.
- Adolescents completing the PRO questionnaires may be helped by their parents/caregivers for the reading and the understanding of the instructions, a word or a question of the questionnaires if they encounter difficulties to answer. However, adolescents (not applicable for those aged ≥ 6 and <12 years) should answer the question themselves; parents/caregivers should not influence nor interpret their child's answer. Parents/caregivers should not select any of the response choices on behalf of their child; only help on transcribing accurately the answers will be allowed.
- The maximum amount of blood collected from each participant over the duration of the study, including any extra assessments that may be required, will not exceed 230 mL for adults, 195 mL for adolescents, and 87 mL for children with weight ≥ 20 to <30 kg or 71 mL for children with weight ≥ 15 to <20 kg. Repeat or unscheduled samples may be taken for safety reasons or for technical issues with the samples.
- In light of the public health emergency related to COVID-19 (or in case of any other pandemic requiring public health emergency), the continuity of clinical study conduct and oversight may require implementation of temporary or alternative mechanisms, eg, phone contact, virtual visits, online meetings, use of local clinic or laboratory locations, and home visits by skilled staff. Implementation of such mechanisms may differ country by country, depending on country regulations and local business continuity plans.

Additionally, no waivers to deviate from protocol enrollment criteria due to COVID-19 (or any other pandemic) will be granted. All temporary mechanisms utilized, and deviations from planned study procedures in response to COVID-19 are to be documented as being related to COVID-19 and will remain in effect only for the duration of the public health emergency.

8.1 EFFICACY ASSESSMENTS

8.1.1 Computerized tomography scans

For both LMK scores, three-dimensional volumetric measurement of the sinuses [REDACTED] [REDACTED] the same acquisitions (sequences) will be used for centralized imaging data assessments and scoring by an independent physician reviewer for the imaging data

8.1.1.1 Lund Mackay score

Computerized tomography scans using the LMK scores allows the assessment of sinus opacification.

The CT scan LMK staging system represents the most widely established method of sinus CT scoring in clinical trials. Lund Mackay total score is based on assessment of the CT scan findings for each sinus area (maxillary, anterior ethmoid, posterior ethmoid, sphenoid, and frontal sinus on each side). The extent of mucosal opacification is rated on a 3-point scale ranging from 0 = normal to 2 = total opacification. In addition, the ostiomeatal complex is graded as 0 = not occluded, or 2 = occluded. The maximum score is therefore 12 per side for a maximum total score of 24, corresponding to the sum of all sinuses and the ostiomeatal unit. This scoring system has been validated in several studies (31, 32, 33).

Computed tomography scans should be performed anytime during the screening period before first administration of IMP at Visit 2 (baseline CT data), at Visit 5 (Week 24), and Visit 7 (Week 52). Whenever possible, a cone beam CT scan should be utilized. In countries for which a specific approval procedure for the CT scan is required by a different committee than the local Independent Ethics Committee (IEC)/Institutional Review Board (IRB), these countries will be exempted from all the planned study CT scans until approval from these committees is received. A 3-month window is required between 2 CT scans in screening period if a participant needs to be rescreened. If Participant who discontinue the study intervention prematurely, the CT scan will be performed as soon as possible, with all other assessments normally planned in EOT Visit (Visit 7). Week 24 CT scan is not required for adolescents/children. In any case, participants may not have more than 3 CT scans during the study. If a participant needs to have CT scan around the time of surgery the next scheduled CT scan per protocol does not need to occur after surgery for AFRS.

The CT scan will be performed locally and centrally reviewed in a pre-specified manner as described in the Image Acquisition Standards (IAS) and Image Interpretation Standards (IIS) and the SoA (Section 1.3).

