b Participants who discontinue the study treatment prematurely (prior to completing the 52-week treatment period) will perform the EOT assessments at the time of discontinuation to assure a complete clinical assessment in close temporal proximity to the premature termination of study treatment. In addition, to allow assessment of participant outcomes over the stipulated study period, participants will be asked and encouraged to complete all remaining study visits and participate in all assessments according to the visit schedule.

c If a participant discontinues treatment period prematurely before Week 40 but completes follow-up to Week 52, he/she will be considered to have completed the study.

d Consent to be obtained for optional procedures (whole blood DNA and whole blood RNA sampling and serum/plasma sampling for archival; HIV test if specific consent locally required, spirometry for children).

e Past medical history including allergic comorbidities (asthma, aspirin sensitivity, allergic rhinitis etc). Surgeries will be assessed including type and dates of sino-nasal surgeries, in the past. Systemic corticosteroids (SCS) use (number of courses, doses, way of administration and duration) in the past 2 years before V1 and/or contraindication/intolerance to SCS, as well as long-term antibiotics use (>2 weeks) in the previous year will be entered in the eCRF. Fungal stain assessment (positive/negative/not done).

f Details on actual or planned date for surgery type and outcome (whenever possible) of surgery will be recorded in a specific eCRF page. If surgery is performed during the study treatment period or follow-up an AE or SAE page will be completed. Participants will be discontinued from study treatment and assessed as soon as possible using the procedures normally planned for the EOT Visit. If surgery is scheduled after the planned end of study, a follow-up contact(s) may be required to document the surgery date and outcome.

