g In case of emergency (eg, natural disaster, pandemic) remote visit (except for Baseline, Week 24 and Week 52) could be considered (eg, Home nursing, Telehealth) and will be documented in the participant's study file. Arrangements could also be made for qualified site personnel and/or health care professionals (eg, visiting nurse service) to collect study samples, administer IMP at participant's home or perform study examinations as needed. "Coronavirus Disease 2019" (COVID-19) pandemic will have an impact on the conduct of clinical trials, some lab tests and clinical assessment procedures can be considered to be conducted locally per local regulation requirement.

- h* Refer to [Section 4 Study Design](#) for details on treatment arms. IMP will be administered after completion of all scheduled clinical assessments and sample collections at the visit or at home.
 - i* Nasal endoscopy (including use of decongestants before the procedure): The participant will be considered eligible based on a V1 central reading followed by a V2 local reading of NPS score of 2 out of 4 for unilateral polyps or 3 out of 8 for bilateral polyps.
 - j* Assessments/procedures should be conducted in the following order: Patient-Reported outcome (PRO), Investigator assessments, safety and laboratory assessments (including sample collection for ADA, PK, biomarker, and optional archival serum/plasma, DNA and RNA), and administration of IMP. Questionnaires in paper form are not permitted; only electronic form is allowed.
 - k* CT scan should be performed during screening period before first administration of IMP, at V5 (Week 24 if accepted per local EC requirement) and at V7 (Week 52), and central reading will be used for comparison baseline (BL) to Week 52 for the primary analysis and at EOT. In countries for which a specific approval procedure for the CT scan is required by a different committee than the IEC/IRB, these countries will be exempted from all the planned study CT scans until approval from these committees is received. If participant need to have CT scan around the time of surgery the next scheduled CT scans per protocol do not need to occur after a surgery for AFRS. In any case participants may not have more than 3 CT scans during the study.

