Any abnormal laboratory value will be immediately rechecked for confirmation within a reasonable timeframe as assessed by the Investigator before making a decision of definitive discontinuation of the IMP for the concerned participant.

Handling of participants after definitive intervention discontinuation

If participants no longer wish to take the IMP, they will be encouraged to remain in the study.

The Investigators should discuss with them key visits to attend. The value of all their study data collected during their continued involvement will be emphasized as important to the public health value of the study.

Participants who withdraw from the study intervention should be explicitly asked about the contribution of possible AEs to their decision, and any AE information elicited must be documented.

Participants will be followed-up according to the study procedures specified in this protocol up to the scheduled date of study completion, or up to recovery or stabilization of any AE to be followed-up as specified in this protocol, whichever comes last.

Participants who discontinue the study intervention prematurely (prior to completing the 52-week treatment period) will perform, as soon as possible, the early termination visit with all assessments normally planned for the end of treatment (EOT) Visit (Visit 7) (refer [Section 8.1.1](#)) including a pharmacokinetics sample, if appropriate, to assure a complete clinical assessment in close temporal proximity to the premature termination of study treatment is available.

In addition, and to allow assessment of participant outcomes over the stipulated study period, participants will be asked and encouraged to complete all remaining study treatment visits, and participate in all assessments according to the visit schedule with a ± 3 day window. Under exceptional circumstances when a participant cannot come to the site for a scheduled visit, a phone contact can be made. During the phone contact, at least information about AEs, concomitant medication, and status of AFRS should be collected.

All cases of definitive intervention discontinuation must be recorded by the Investigator in the appropriate pages of the eCRF when considered as confirmed.

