3.2.2 Main analytical approach

The primary endpoint will be analyzed with the estimand defined according to the following attributes:

- Endpoint: Change from baseline in LMK score at Week 52
- Treatment condition: dupilumab will be compared to placebo
- Analysis population: ITT population
- Intercurrent events (IE):
 - The following intercurrent events will be handled with a composite strategy; data after the IE will be excluded and the worst post-baseline value on or before the start of the IE will be assigned to the Week 52 value (WOCF); for participants with no post-baseline values, the baseline value will be used.
 - Undergo/plan to undergo surgery for AFRS prior to Week 52
 - Taking SCS for any reason prior to Week 52

- The following IEs will be handled with the treatment policy strategy (without IEs that need to be handled with composite strategy). All assessments after starting such IE will be included.
 - Discontinuing the study intervention
 - Taking antifungals or other prohibited/rescue medications
- Population-level summary:

The primary endpoint will be analyzed using an analysis of covariance (ANCOVA) model with the baseline LMK score, intervention group, time from last surgery (≤ 2 years, >2 years), and region (Americas: Argentina, USA, Canada; Asia: China, Japan, India, Turkey, Saudi Arabia) as covariates, with intercurrent event strategies and missing data handling as defined in [Table 3](#).

Data of participants who undergo/plan to undergo surgery for AFRS or take SCS for any reason on or before Week 52 will be excluded from analysis after the IE, and the worst postbaseline value on or before the start of IE will be used to assign missing endpoint value (for participants whose postbaseline values are all missing, the baseline will be used to impute). Participants who discontinue the intervention prematurely are encouraged to follow the planned clinical visits and in those participants who did not have any of the above IE, all data collected after intervention discontinuation will be used in the analysis. For these participants, missing data may still happen despite all efforts to collect the data after treatment discontinuation. A multiple imputation (MI) approach will be used to impute missing endpoint value, and this MI method will use all participants excluding participants with the above IE. The imputation number will be 40.

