Each of the imputed complete data will be analyzed by fitting an ANCOVA model as described above. Statistical inference obtained from all imputed data will be combined using Rubin's rule. Descriptive statistics including number of participants, mean, standard error, and least squares (LS) mean changes (and standard error) will be provided. In addition, difference of the dupilumab group against placebo in LS means and the corresponding 95% confidence intervals (CI) will be provided along with the p-value.

A separate summary of primary endpoint will be provided for pediatric patients.

The multiple imputation and analysis model for the primary analysis of change from baseline in LMK values will be built with the following sample SAS code.

1. 40 datasets with a monotone missing pattern will be obtained, induced by Markov Chain Monte Carlo (MCMC) method on all participants excluding participants who undergo/plan to undergo surgery for AFRS or take SCS for any reason on or before Week 52.

```
proc mi data=ads out=monotone n impute=40 seed=16724;
  where wocfl='N';
  var time region trt01p value0 value24 value52;
  mcmc chain=multiple impute=monotone;
run;
```

2. For each of the imputed datasets with monotone missing pattern in step 1, the remaining missing data at baseline and post-baseline visits will be imputed using regression method for the monotone missing pattern with adjustment for covariates including time from last surgery (≤ 2 years, > 2 years), region (Americas, Asia) and intervention group.

```
proc mi data=monotone out=dat_mi nimpute=1 seed=16724 minimum=... 0 0 0  
maximum=... 24 24 24; /*LMK score range is 0-24*/
```

```
    by _imputation_;  
    class time region trt01p;  
    var time region trt01p value0 value24 value52;  
    monotone reg (/details);  
run;
```

3. Each of the 40 imputed datasets will be merged with one dataset imputed by WOCF approach, and then be analyzed using the main statistical model. These 40 imputed datasets will be saved.

```
%macro w1;  
    %do i=1%to 40;  
        data wocf&i.;  
        set ads;  
        where wocffl='Y';  
        _imputation_=&i.;  
        run;  
    %end;  
    data wocf_all;  
        set %do j=1 %to 40; wocf&j. %end;;  
        run;  
    %mend w1;  
  
%w1;  
  
data mi;  
    set dat_mi wocf_all;  
run;  
  
proc sort data=mi; by _imputation_; run;  
  
proc glm data=mi;  
    by _imputation_;  
    class time region trt01p;  
    model change=time region trt01p value0;  

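### For adults who have the Week 24 CT, a separate scan at early discontinuation uses up the three-scan cap and rules out the Week 52 CT that the primary estimand needs

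*Protocol*

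**What the plan says.** Protocol 8.1.1.1 schedules CT at screening, Week 24 and Week 52 for adults. The Week 24 scan is not required in adolescents and children. For participants who stop IMP early, the same section says that "the CT scan will be performed as soon as possible, with all other assessments normally planned in EOT Visit (Visit 7". It then caps the total: "In any case, participants may not have more than 3 CT scans during the study". SoA footnote k repeats the limit: "In any case participants may not have more than 3 CT scans during the study".

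Follow-up after stopping IMP is still requested. Under SoA footnote b, "participants will be asked and encouraged to complete all remaining study visits and participate in all assessments according to the visit schedule". Section 7.1.1 likewise asks participants to "complete all remaining study treatment visits, and participate in all assessments according to the visit schedule".

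The primary estimand handles discontinuation of IMP by treatment policy. In SAP 3.2.2, for participants without SCS or actual or planned surgery, "all data collected after intervention discontinuation will be used in the analysis". The SAP accepts that "missing data may still happen despite all efforts to collect the data after treatment discontinuation" and fills those gaps by multiple imputation.

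SAP 5.4, Table 7, assigns CT scans dated after first dose and up to Day 266 to Week 24, and all later ones to Week 52. Where two scans share a window, the one closer to the target day is used and a tie goes to the later scan.

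**The concern.** The stopping CT, the request to stay on the visit schedule and the cap cannot all be met for one group: adults who have the Week 24 CT, stop IMP early, have neither SCS nor actual or planned surgery, and have a stopping CT separate from a scheduled scan. The stopping CT is worded as something that will happen, while the remaining assessments are encouraged. A site that follows the text therefore does the stopping scan and has none left for Week 52.

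What is lost is the primary measurement in exactly the participants for whom treatment policy calls for the observed Week 52 outcome. The Week 52 volumetric CT endpoint, which is in the SAP 3.5 testing order, relies on the same acquisitions (Protocol 8.1.1). Imputation meant for data that could not be collected would here replace data that the protocol does not allow to be collected.

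**Working it through.** **Inputs.** Cap: 3 scans (Protocol 8.1.1.1, SoA footnote k). Screening is listed as part of the study period in Protocol 4.1, so the baseline CT counts. CT targets: Day 169 (Week 24) and Day 364 (Week 52), with the boundary after Day 266 (SAP Table 7). Visit window: ±3 days (SoA).

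**1. The plan's own count.** Screening 1 + Week 24 1 + Week 52 1 = 3, which equals the cap. There is no spare scan for an adult.

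**2. With a separate stopping CT.** Screening 1 + Week 24 1 + stopping 1 + Week 52 1 = 4, against a cap of 3. The order of the stopping and Week 24 scans does not matter, so a stop before Week 24 meets the same limit if the Week 24 CT is also taken. Without a Week 24 CT, as is permitted for adolescents and children, the count is 1 + 1 + 1 = 3 and the Week 52 CT fits.

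**3. What the SAP windows then do.** Take the Week 24 CT on Day 169 and no Week 52 scan. Table 7 works on scan dates, not on the dates when IMP was stopped.

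| Stopping CT dated | Check | Week 24 value | Week 52 value |
|---|---|---|---|
| Day 60 | 169 − 60 = 109 days from target, against 0 | Day 169 scan | Imputed |
| Day 200 | 200 − 169 = 31 days from target, against 0 | Day 169 scan | Imputed |
| Day 300 | 300 > 266; 364 − 300 = 64 days early | Day 169 scan | Day 300 scan, or imputed if it is not accepted as a measurement for Table 7 |

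The same rules were applied to every stopping-scan date from Day 2 to Day 360. With the Week 24 CT on Day 169, no stopping scan up to Day 266 supplies a visit value. With the Week 24 CT on Day 166 or Day 172, a stopping scan displaces it only on Days 167–172 or Days 167–171 respectively, and Week 52 is still missing.

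**4. How early a stopping scan can stand in for Week 52.** The Week 52 visit window opens on Day 364 − 3 = 361. Stopping scans dated Day 267 to Day 360 (360 − 267 + 1 = 94 days) would be between 364 − 360 = 4 and 364 − 267 = 97 days early.

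**5. Whether the window boundary is at fault.** The midpoint of the two targets is (169 + 364)/2 = 266.5, so the boundary is the natural one. If both a Day 300 and a Day 364 scan existed, the distances would be 64 and 0 and the Day 364 scan would be used. The problem is the absent scan.

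**6. What the imputation uses.** The SAP code lists "var time region trt01p value0 value24 value52": time from last surgery, region, treatment, and LMK at baseline, Week 24 and Week 52. There is no term for discontinuation of IMP, and an unused stopping scan does not enter the model.

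**The case against.** **The stopping CT may be the Visit 7 scan brought forward.** The SoA labels Week 52 as end of treatment, the cap is worded to apply in every case, and the remaining assessments are only encouraged. On that reading the instructions are ranked and do not contradict each other. This is a fair reading and it removes the breach of the cap. It does not restore a Week 52 observation.

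**The SAP already has a rule.** A reader might infer that SAP 5.4 says nothing usable about the stopping scan. The documents do not support that. Apart from a few days around Day 169, a scan dated up to Day 266 gives the same result however it is classed. For later scans, the opening of 5.4 applies the windows to scheduled and unscheduled visits and names efficacy among the analyses. A stopping CT required by the protocol can also reasonably be called scheduled. The natural reading is therefore that a scan after Day 266 becomes the Week 52 value. Mild doubt remains because the efficacy paragraph assigns only scheduled measurements and the unscheduled-visit paragraph names only laboratory data and vital signs.

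**Missing data after discontinuation are foreseen.** This is true, and the imputation draws on the participant's own baseline and Week 24 LMK, which limits the damage. The provision is framed around data lost despite efforts to collect them, which is not the situation here.

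**Few people are affected.** Protocol 7.1.1 describes definitive discontinuation as rare. This stands and sets the severity.

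**Conclusion.** The conflict holds for the group described: the cap, the stopping CT and the requested Week 52 CT cannot all be met. The visible waivers of a CT concern surgery, pending committee approval, local acceptance of the Week 24 scan, and adolescents and children at Week 24. None says which scan gives way after discontinuation of IMP alone. Protocol 8.1.1.1 refers to imaging standards that are not among the documents and might address it.

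The consequence is a Week 52 LMK value that is either imputed without a discontinuation term or, for stopping scans dated after Day 266, most naturally an observation up to 97 days early.

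A reader might go further and infer that the primary result is materially biased, or that everyone who stops IMP loses the Week 52 CT. Neither follows. The documents give no expected number of early discontinuations and nothing from which the size or direction of bias could be derived. Participants without a Week 24 CT have room under the cap, and those with SCS or surgery are handled by worst observation carried forward. With discontinuation described as rare and stated power above 99% for the primary endpoint (SAP 3.9), the effect is on the estimate and is probably small. Severity: minor.

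**What to change.** - **Protocol.** Reconcile 8.1.1.1, Section 7.1.1 and SoA footnotes b and k so that, within the existing three-scan cap, the Week 52 CT remains obtainable for participants who stop IMP but stay in the study.
- **SAP 5.4.** State in one sentence whether a discontinuation CT dated after Day 266 counts as the Week 52 value. Leave the Day 266/267 boundary as it is.
- **Reporting.** Give by arm the number of Week 52 LMK values that are discontinuation scans, and the number imputed after discontinuation.
- **Sensitivity analysis.** Unless one is already planned in SAP text not shown, add one that sets discontinuation scans dated before Day 361 to missing at Week 52, with the same multiple imputation.

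The cost is a protocol clarification, one SAP sentence, one count and one extra run of existing code, with no additional scan. The downside is that a few participants may have no separate CT at the time of stopping. Scans already taken cannot be changed. The documents do not show whether the database has been locked: before lock, the SAP items can still be prespecified; after it, they should be reported as post hoc.
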